better, get sympathy, or get something else to happen)? (Self-Injurious Behavior without suicidal intent)						
If yes, describe:						
Has subject engaged in Non-Suicidal Self-Injurious Behavior?						
Interrupted Attempt:	Yes No					
When the person is interrupted (by an outside circumstance) from starting the potentially self-injurious act (if not for that, actual						
attempt would have occurred).						
Overdose: Person has pills in hand but is stopped from ingesting. Once they ingest any pills, this becomes an attempt rather than	Total # of interrupted					
an interrupted attempt. Shooting: Person has gun pointed toward self, gun is taken away by someone else, or is somehow						
prevented from pulling trigger. Once they pull the trigger, even if the gun fails to fire, it is an attempt. Jumping: Person is poised						
to jump, is grabbed and taken down from ledge. Hanging: Person has noose around neck but has not yet started to hang - is						
stopped from doing so.						
Has there been a time when you started to do something to end your life but someone or something stopped you						
before you actually did anything? If yes, describe:						
Aborted Attempt:	Yes No					
When person begins to take steps toward making a suicide attempt, but stops themselves before they actually have engaged in any	103110					
self-destructive behavior. Examples are similar to interrupted attempts, except that the individual stops him/herself, instead of						
being stopped by something else.	Total # of					
Has there been a time when you started to do something to try to end your life but you stopped	aborted					
yourself before you actually did anything?						
If yes, describe:						
Preparatory Acts or Behavior:	Yes No					
Acts or preparation towards imminently making a suicide attempt. This can include anything beyond a verbalization or thought,						
such as assembling a specific method (eg, buying pills, purchasing a gun) or preparing for one's death by suicide (eg, giving						
things away, writing a suicide note).						
Have you taken any steps towards making a suicide attempt or preparing to kill yourself (such as collecting pills,						
getting a gun, giving valuables away or writing a suicide note)?						
If yes, describe:						
Suicidal Behavior:	Yes No					
Suicidal behavior was present during the assessment period?						
Completed Suicide:	Yes No					
Compicion Suicine.						
Answer for Actual Attempts Only	Most Lethal					
	Attempt					
	Date:					

[figure not shown]
Actual Lethality/Medical Damage: 0. No physical damage or very minor physical damage (eg, surface scratches).	Enter Code
 Minor physical damage (eg, lethargic speech; first-degree burns; mild bleeding; sprains). Moderate physical damage; medical attention needed (eg, conscious but sleepy, somewhat responsive; second-degree burns; 	
bleeding of major vessel). 3. Moderately severe physical damage; medical hospitalization and likely intensive care required (eg, comatose with reflexes	
intact; third-degree burns less than 20% of body; extensive blood loss but can recover; major fractures).	
4. Severe physical damage; medical hospitalization with intensive care required (eg, comatose without reflexes; third-degree burns over 20% of body; extensive blood loss with unstable vital signs; major damage to a vital area).	
5. Death	
Potential Lethality: Only Answer if Actual Lethality=0	Enter Code
Likely lethality of actual attempt if no medical damage (the following examples, while having no actual medical damage, had	
potential for very serious lethality: put gun in mouth and pulled the trigger but gun fails to fire so no medical damage; laying on	
train tracks with oncoming train but pulled away before run over).	
0 = Behavior not likely to result in injury	
1 = Behavior likely to result in injury but not likely to cause death	
2 = Behavior likely to result in death despite available medical care	

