4.4 Exclusion Criteria

The following are criteria for exclusion from participating in the study:

Psychiatric Criteria

- 1. Four or more episodes of a mood disturbance within the 12 months before Visit 1.
- 2. Another psychiatric disorder other than bipolar disorder with the exception of specific phobias.
- 3. Currently meeting DSM-5 criteria for any of the following:
 - a. Major/minor neurocognitive disorder, amnestic, or other neurocognitive disorders
 - b. Schizophrenia, schizoaffective disorder, and other psychotic disorders
 - c. Intellectual development disability
- 4. Known or suspected borderline of antisocial personality disorder or other DSM-5 personality disorders of sufficient severity to interfere with participation in this study.
- 5. History of meeting DSM-5 criteria for substance-related disorders (ie, use disorders except caffeine- and tobacco-related) within 3 months prior to Visit 1.
- 6. Positive result at Visit 1 from the urine drug screen (UDS). Patients with a positive UDS at Visit 1 for opiates, cannabinoids, amphetamines, barbiturates, or benzodiazepines may be enrolled if all of the following are satisfied:
 - a. The drug was used for a legitimate medical purpose;
 - b. The drug can be discontinued prior to participation in the study (except for benzodiazepines which may be continued if the patient has been taking a stable dose [ie, lorazepam up to 2 mg/d or its benzodiazepine equivalent] for at least 1 month prior to Visit 1 or if used as rescue during washout); and
 - c. A repeat UDS must be performed prior to Visit 2 and must be negative, except benzodiazepine use as described in 6(b).
- 7. History of intolerance or hypersensitivity to cariprazine or rescue medications.

- 8. The patient is at imminent risk of injuring self or others or causing significant damage to property, as judged by the investigator.
- 9. The patient represents a suicide risk, as determined by meeting any of the following criteria:
 - a. Patient made a suicide attempt within the past year before Visit 1
 - b. Patient had a score of 4 or greater on Item 10 of the MADRS at Visit 1 (Screening) or Visit 2 (Baseline)
 - c. Significant risk, as judged by the investigator, based on the psychiatric interview or information collected in the C-SSRS at Visit 1 (Screening) or Visit 2 (Baseline)

Treatment-Related Criteria:

- 10. Patient had electroconvulsive therapy in the 3 months prior to Visit 1.

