6.6.7.2 Columbia-Suicide Severity Rating Scale

The C-SSRS is a clinician-rated instrument that reports the severity of both suicidal ideation and behavior. Suicidal ideation is classified on a 5-item scale: 1 (wish to be dead), 2 (nonspecific active suicidal thoughts), 3 (active suicidal ideation with any methods [not plan] without intent to act), 4 (active suicidal ideation with some intent to act, without specific plan), and 5 (active suicidal ideation with specific plan and intent). The C-SSRS also captures information about the intensity of ideation, specifically the frequency, duration, controllability, deterrents, and reasons for the most severe types of ideation. Suicidal behavior is classified on a 5-item scale: 0 (no suicidal behavior), 1 (preparatory acts or behavior), 2 (aborted attempt), 3 (interrupted attempt), and 4 (actual attempt). More than 1 classification can be selected provided they represent separate episodes. For actual attempts only, the actual or potential lethality is classified for the initial, most lethal, and most recent attempts. The C-SSRS will be completed at all study visits. At Visit 1 (Screening), the C-SSRS will be completed for the patient's lifetime history of suicidal ideation and behavior. At all other visits the C-SSRS will be completed for ideation and behavior since the previous visit.

The C-SSRS will be completed by a trained rater with extensive professional training.

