8.4.2 Baseline (Visit 2)

The following procedures will be carried out at Baseline/Visit 2:

- Assess inclusion/exclusion criteria
- Review concomitant medications
- Assess YMRS, MADRS, CGI-S, PSP, and C-SSRS
- Evaluate EPS symptoms (AIMS/BARS/SAS)
- Collect vital signs measurements (including weight)
- Obtain consent for and/or collect blood for pharmacogenetic sampling (a single sample can be obtained any time between Visit 2 and Visit 7, inclusive)
- Review and assess AEs and SAEs
- Access IWRS to dispense IP

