12.11 Columbia-Suicide Severity Rating Scale

COLUMBIA-SUICIDE SEVERITY RATING SCALE

(C-SSRS)

Baseline Version 1/14/09

Posner, K.; Brent, D.; Lucas, C.; Gould, M.; Stanley, B.; Brown, G.; Fisher, P.; Zelazny, J.; Burke, A.; Oquendo, M.; Mann, J.

Disclaimer:

This scale is intended for use by trained clinicians. The questions contained in the Columbia-Suicide Severity Rating Scale are suggested probes. Ultimately, the determination of the presence of suicidality depends on clinical judgment.

Definitions of behavioral suicidal events in this scale are based on those used in The Columbia-Suicide History Form, developed by [name] and [name], Conte Center for the Neuroscience of Mental Disorders (CCNMD), New York State Psychiatric Institute, [name]. (Oquendo M. A., Halberstam B. & Mann J. J., Risk factors for suicidal behavior: utility and limitations of research instruments. In M.B. First [Ed.] Standardized Evaluation in Clinical Practice, pp. 103-130, 2003.)

For reprints of the C-SSRS contact [name]., New York State Psychiatric Institute, [name]; inquiries and training requirements contact [contact]

SUICIDAL IDEATION	
Ask questions 1 and 2. If both are negative, proceed to "Suicidal Behavior" section. If the answer to question 2 is "yes," ask questions 3, 4 and 5. If the answer to question 1 and/or 2 is "yes", complete "Intensity of Ideation" section below.	Lifetime: Time He/She Felt Most Suicidal
1. Wish to be Dead Subject endorses thoughts about a wish to be dead or not alive anymore, or wish to fall asleep and not wake up. Have you wished you were dead or wished you could go to sleep and not wake up? If yes, describe:	Yes No
2. Non-Specific Active Suicidal Thoughts General, non-specific thoughts of wanting to end one's life/commit suicide (eg, "I've thought about killing myself") without thoughts of ways to kill oneself/associated methods, intent, or plan.	Yes No
Have you actually had any thoughts of killing yourself? If yes, describe: 3. Active Suicidal Ideation with Any Methods (Not Plan) without Intent to Act	Yes No

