11.0 SAFETY ANALYSES

The safety analyses will be performed for the OL safety, OL SFU and DB safety Population. The summarization will be overall for the OLTP in the OL safety population and OL SFU period in the OL SFU population, and by treatment group for the DB period and the DB SFU period in the DB safety population. The summarization for the OLTP will use the OL safety population as the denominator. The summarization for the DBTP will use the DB safety population as the denominator. The summarization for the OL SFU period or DB SFU period will use the OL SFU Safety Population or the DB safety population as the denominator respectively.

Safety parameters will include adverse events (AEs), clinical laboratory parameters, vital signs, Electrocardiogram (ECG) parameters, ophthalmology parameters, Columbia–Suicide Severity Rating Scale (C-SSRS), EPS scales, including Abnormal Involuntary Movement Scale (AIMS), Barnes Akathisia Rating Scale (BARS), and Simpson-Angus Scale (SAS), and prolactin level.

For each safety parameter, the last assessment made before the first dose of OL IP will be used as the baseline for all analyses of that safety parameter, unless stated otherwise. Continuous variables will be summarized by number of patients and mean, SD, median, minimum, and maximum values. Categorical variables will be summarized by number and percentage of patients.

The derived visits in the DBTP will use the same strategy as described in Section 10.0. The detailed week mapping windows is provided in Section 16.1.

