11.5.2 Columbia-Suicide Severity Rating Scale

For the C-SSRS, the number and percentage of patients with suicidal ideation or suicidal behavior, as recorded on the C-SSRS scale, will be presented overall for the OLTP and by treatment group for the DBTP. The distribution of response for most severe suicidal ideation and suicidal behavior during the lifetime history, the OLTP, and the DBTP will be presented overall for the OLTP and by treatment group for the DBTP. Supportive listings will be provided, including the PID number, treatment group (for DBTP only), visit number, lifetime history, and postbaseline values for each patient. Intensity of ideation, suicidal behavior type, and lethality of suicidal behavior will also be included in these listings. Listings of all AEs occurring in patients who have suicidal ideation or suicidal behavior during OLTP and DBTP will also be provided.

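### SAP 11.5.2 does not use the pre-dose Visit 2 C-SSRS rating, so its open-label suicidality percentage mixes persisting ideation with new or worsened ideation

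*Protocol*

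**What the plan says.** **Collection.** Protocol 6.6.7.2 sets two recall periods: "At Visit 1 (Screening), the C-SSRS will be completed for the patient's lifetime history of suicidal ideation and behavior", and "At all other visits the C-SSRS will be completed for ideation and behavior since the previous visit". The ideation page of the screening form (Attachment 12.11, Baseline version) has the single column "Lifetime: Time He/She Felt Most Suicidal". The scale is rated again before open-label drug is dispensed: Protocol 8.4.2 lists "Assess YMRS, MADRS, CGI-S, PSP, and C-SSRS" at Visit 2.

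**Baseline rule.** SAP 11.0 names the C-SSRS among the safety parameters and says that, unless stated otherwise, "the last assessment made before the first dose of OL IP will be used as the baseline for all analyses of that safety parameter". For the C-SSRS this is normally the Visit 2 rating.

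**Analysis.** SAP 11.5.2 plans "the number and percentage of patients with suicidal ideation or suicidal behavior, as recorded on the C-SSRS scale", overall for the open-label period (OLTP) and by arm for the double-blind period (DBTP). It adds: "The distribution of response for most severe suicidal ideation and suicidal behavior during the lifetime history, the OLTP, and the DBTP will be presented". The listings it describes carry lifetime history and postbaseline values. Protocol 7.3.4.5.2 has the same three periods. Under SAP 7.1 the OLTP begins with the first open-label dose.

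**Entry.** Exclusion criterion 9b in Protocol 4.4 applies where the "Patient had a score of 4 or greater on Item 10 of the MADRS at Visit 1 (Screening) or Visit 2 (Baseline"). Criterion 9c also excludes patients whom the investigator judges to be at significant risk from the psychiatric interview or the C-SSRS at either visit.

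**The concern.** The OLTP has one arm. With no concurrent control, the patient's own pre-dose state is the only reference for what happened to suicidality after cariprazine was started. The plan collects that reference and defines it as the baseline, but the section that analyzes the C-SSRS does not call on it.

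Patients enter in an acute episode. Those in the depressive group need a MADRS total of at least 23, and low-grade suicidal thoughts do not exclude them. If such thoughts are present at Visit 2 and again at Visit 3 (Day 8), the patient counts toward the OLTP percentage exactly as does a patient whose thoughts began after the first dose. A reader of the study report would want to know how many patients became suicidal or got worse on open-label drug. The planned summaries do not answer that question.

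**Working it through.** No arithmetic is needed to establish the gap. It follows from setting the sections side by side.

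1. **Which C-SSRS rating is confined to the days just before dosing?** Visit 1 covers the lifetime. Visit 2 covers Visit 1 to Visit 2. Visit 3 covers the interval since Visit 2. Only Visit 2 qualifies.
2. **Which tabulated period contains it?** The OLTP starts at the first dose, so a pre-dose rating lies outside it. It is not the lifetime rating, which is taken at Visit 1. It therefore belongs to none of the three periods in SAP 11.5.2.
3. **Does another rule in that section bring it in?** No. There is no shift table, no change from baseline and no definition of new or worsened ideation.
4. **Is that usual in this SAP?** No. SAS and BARS have treatment-emergent definitions tied to the baseline score (11.5.3). Laboratory and ECG flags require a baseline value that was not already flagged (11.2, 11.4). Vital-sign flags require a change from baseline, and hypertension status has shift tables (11.3). An adverse event must begin or worsen after the first open-label dose (11.1).
5. **Can carry-over occur?** Yes. Item 10 scores of 0 to 3 pass criterion 9b. In Attachment 12.3 the step between scores 1 and 3 already describes fleeting suicidal thoughts. Remission cannot be declared before Day 15, so persistence at Day 8 is plausible. Criteria 8, 9a and 9c remove imminent risk, attempts in the past year and significant risk; what remains is lower-grade ideation.

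Four hypothetical patients show the effect (C-SSRS ideation type, 0 = none):

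| Patient | Visit 2 | Worst in OLTP | In planned any-ideation count | Relative to Visit 2 |
|---|---|---|---|---|
| A | 2 | 2 | yes | persisting |
| B | 0 | 2 | yes | new |
| C | 1 | 4 | yes | worsened |
| D | 2 | 0 | no | resolved |

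The planned count is 3 of 4; the new-or-worsened count is 2 of 4. The planned severity distribution sets C apart but puts A and B in the same category. The lifetime row does not help: it is a separate distribution of the worst point ever, and A and B could share the same lifetime value.

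**Recall windows, which matter for the fix.** Visit 1 falls on Days -7 to -1 and Visit 2 on Day 1, with up to 3 days' allowance. The Visit 2 recall thus runs from about 1 day to 7 + 3 = 10 days. The OLTP lasts up to 16 weeks, or 16 × 7 = 112 days.

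**Size.** The mixture depends on the share of patients with ideation at Visit 2 and the share in whom it persists after dosing. The documents give neither.

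**The case against.** Several points on the other side stand.

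- **The information exists.** Visit 2 and all later ratings are collected, and SAP 16.3 puts all assessments in the data listings. A reader might infer that the trial cannot say how many patients worsened. That goes too far: the count can be derived, but it is not among the summaries SAP 11.5.2 specifies.
- **Other pre-dose data exist.** The screening form also dates the most recent attempt, and MADRS item 10 rates suicidal thoughts over the past week at Visits 1 and 2. Pre-treatment information is therefore not limited to the lifetime worst point. Neither source, however, gives a C-SSRS reference for the C-SSRS tables.
- **The SAP makes no causal claim.** SAP 11.5.2 reports ideation recorded in a period and does not call it treatment-emergent. A reader might infer that carried-over ideation is being labelled a drug effect; the text does not say so. The fault is only that the two kinds are not separated.
- **Adverse event tables identify new or worsened events.** They do, for suicidality reported as an adverse event. Protocol 9.1.1 tells sites not to report worsening that is captured as an efficacy variable and is unequivocally disease progression or lack of efficacy, unless it exceeds the expected course. Suicidal thoughts are a MADRS item, so this route is partial.
- **Table specifications are in a separate document** (SAP 4.0), which is not available here. A baseline row there cannot be ruled out. The SAP text should still state the comparison.

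**Conclusion.** The gap is real and limited. SAP 11.5.2 leaves out the pre-dose rating that SAP 11.0 designates as baseline, so the single-arm OLTP percentage combines persisting with new or worsened ideation. This conclusion rests on the SAP text and on entry rules that admit lower-grade ideation.

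No size can be attached. A figure in patients would need assumed shares for ideation at Visit 2 and for persistence. Treating everyone with ideation at the first post-dose visit as carry-over would also assume the answer.

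A reader might also infer a bias in the randomized comparison. The documents do not support that: the arms are formed at Visit 12 from patients meeting the same stability criteria, and all arms are summarized by the same rule. No hypothesis test depends on this summary. The consequence is for descriptive safety reporting of the open-label phase, where it still matters because there is no control arm.

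**What to change.** In SAP 11.5.2, for the OLTP:

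- add a Visit 2 (pre-dose) row to the distribution of most severe ideation and behavior;
- add a shift table from the Visit 2 category to the worst OLTP category;
- report the number and percentage of patients with new or worsened ideation or behavior, meaning a higher category than at Visit 2, alongside the existing any-ideation percentage;
- keep lifetime history as background;
- show patients without a Visit 2 rating separately, so that the lifetime rating does not become their baseline by default.

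An equivalent DBTP table by arm, using the last rating before the first double-blind dose (Visit 12), is optional.

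The cost is SAP wording and one or two tables from data already collected; trial conduct does not change. The downside should be stated with the table. A Visit 2 recall of about 1 to 10 days is compared with the worst of up to 16 weeks, so the longer window has more chance to record a high category and the shift leans toward apparent worsening. The optional DBTP table has the same lean, with Visit 12 usually covering about two weeks against up to 39, but under the same rule in every arm.

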12.12 Work Productivity and Activity Impairment Questionnaire: Bipolar Disorder (WPAI-BD)

[figure not shown]
The following questions ask about the effect of your bipolar disorder on your ability to work and perform regular activities. *Please fill in the blanks or circle a number, as indicated.*

Are you currently employed (working for pay)? ____NO __YES If NO, check "NO" and skip to question 6.
 The next questions are about the past seven days, not including today.
 During the past seven days, how many hours did you miss from work because of problems associated with your bipolar disorder? Include hours you missed on sick days, times you went in late, left early, etc. because of bipolar disorder. Do not include time you missed to participate in this study. ____HOURS
 During the past seven days, how many hours did you miss from work because of any other reason, such as vacation, holidays, time off to participate in this study? ____HOURS
 During the past seven days, how many hours did you actually work? HOURS (If "0", skip to question 6)

5) During the past seven days, how much did bipolar disorder affect your productivity while you were working? Think about days you were limited in the amount or kind of work you could do, days you accomplished less than you would like, or days you could not do your work as carefully as usual. If bipolar disorder affected your work only a little, choose a low number. Choose a high number if bipolar disorder affected your work a great deal.

6) During the past seven days, how much did bipolar disorder affect your ability to do your regular daily activities, other than work at a job? By regular activities, we mean the usual activities you do, such as work around the house, shopping, child care, exercising, studying, etc. Think about times you were limited in the amount or kind of activities you could do and times you accomplished less than you would like. If bipolar disorder affected your activities only a little, choose a low number. Choose a high number if bipolar disorder affected your activities a great deal.

